## **Test Product, Dose, and Mode of Administration**

Magrolimab is a humanized monoclonal antibody against CD47, which is administered intravenously (IV).

- R/R Safety and Expansion Cohorts: In the R/R Safety Cohort, magrolimab monotherapy will be administered twice weekly on an intrapatient dose escalation schedule: 1 mg/kg twice weekly for Week 1 (Day 1 and Day 4); 15 mg/kg on Day 8; 30 mg/kg on Day 11 and Day 15; and 30 mg/kg weekly thereafter. For the R/R Expansion Cohort, magrolimab will be administered on a different dose schedule: 1 mg/kg twice weekly for Week 1 (Day 1 and Day 4); 15 mg/kg on Day 8; 30 mg/kg on Day 11 and Day 15; and 30 mg/kg weekly on Day 22 through end of Cycle 2, then 30 mg/kg Q2W starting Cycle 3 and thereafter. For R/R Expansion, azacitidine will be administered according to approved labeling, either subcutaneously (SC) or IV, at the standard dose of 75 mg/m² on Days 1 to 7 of each 28-day cycle.
- R/R MDS Magrolimab Monotherapy Cohort: Magrolimab will be administered twice weekly through Cycle 1 Day 11, and then weekly beginning Cycle 1 Day 15 and thereafter using a similar intrapatient dose escalation schedule as used for the R/R Safety Cohort (1 mg/kg on Day 1 and Day 4, 15 mg/kg on Day 8, 30 mg/kg on Day 11 and Day 15, 30 mg/kg weekly through end of Cycle 2). However, for this subcohort, patients will receive magrolimab after intrapatient dose escalation at 30 mg/kg Q2W starting Cycle 3 and thereafter).
- TN/U Dose Evaluation Cohort: Magrolimab will be administered twice weekly through Cycle 1, Day 11, and then weekly beginning Cycle 1, Day 15, and thereafter using a similar intrapatient dose escalation schedule as used for the R/R Safety Cohort (1 mg/kg on Days 1 and 4; 15 mg/kg on Day 8; 30 mg/kg on Days 11 and 15; and 30 mg/kg weekly thereafter). Azacitidine will be administered according to approved labeling, either SC or IV, at the standard dose of 75 mg/m² on Days 1 to 7 of each 28-day cycle.

- TN/U Expansion Cohort (including MDS Registrational Cohort): As of Amendment 5, RP2DS for magrolimab as determined in the TN/U Dose Evaluation Cohort, is identical to that tested in the R/R Safety Cohort.

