# 3.3.3. TN/U Cohort Dose-limiting Toxicity Evaluation

Dose evaluation decisions will be made by the CTSC based on the first 4 weeks of treatment for each patient, referred to as the "Dose-limiting Toxicity (DLT) Assessment Period." The first patient in each 3+3 dose evaluation cohort must complete at least 2 weeks of treatment before additional patients may be enrolled in the cohort. Subsequent patients may be enrolled simultaneously. The third patient in a cohort must complete the DLT Assessment Period prior to enrolling the next 3 patients at the same dose level. A new patient may be enrolled whenever a patient becomes nonevaluable for DLT. The CTSC may decide whether a fourth patient can be enrolled to the same cohort prior to the first 3 patients completing the DLT Assessment Period, in order to have an extra patient in case that 1 of the 3 earlier patients are not evaluable for DLT or if there is a DLT within the cohort requiring cohort expansion.

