## 3.3.4. TN/U Cohort Definition of DLT-evaluable Patients

Patients in the TN/U Dose Evaluation cohort are considered evaluable for assessment of DLT if EITHER of the following criteria are met during the DLT Assessment Period:

- The patient experienced a DLT at any time after initiation of the first infusion/injection of magrolimab.
- The patient completed at least 4 infusions of magrolimab and 4 infusions/injections of azacitidine.

For the TN/U Dose Evaluation cohort, patients who withdraw before completing the 4-week DLT Assessment Period for reasons other than a DLT, or who do not fulfill either of the criteria above, will not be evaluable for assessment of DLT for dose review decisions and will be replaced in the cohort.

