# 6.2. Dose Modifications, Dose Delays, and Safety Management Guidelines

# 6.2.1. Dose Modification and Delay Guidelines

## 6.2.1.1. Magrolimab

## **Dose Modifications**

Magrolimab may be withheld if treatment-emergent and/or magrolimab-related AEs occur, which include all AEs that constitute a DLT, as defined in Section 3.3.5.

Magrolimab may be reintroduced at a 50% dose reduction if the severity has recovered to Grade  $\leq$  2 within 4 weeks and in the absence of disease progression, with approval from the Medical Monitor. A dose delay for up to 3 days may be permissible if the patient's WBC count is greater than 20 × 10 $^9$ /L (which is applicable to Cycle 1), to allow for oral hydroxyurea or etoposide treatment to reduce the WBC count. Further dose delay due to elevated WBC counts must be discussed and approved by the Medical Monitor.

Patients who experience a Grade 4 or higher AE of hemagglutination and/or microangiopathy related to magrolimab will permanently discontinue magrolimab treatment. Patients who experience Grade 3 hemagglutination and/or microangiopathy will have magrolimab dosing withheld, and may be reintroduced at a 50% dose reduction if the event severity recovers to Grade  $\leq$  1 within 4 weeks and there is no evidence of disease progression.

With one exception, patients who experience a DLT will have their treatment held for up to 4 weeks to allow sufficient time for recovery, but may restart dosing at a lower dose level if they still meet study eligibility criteria. Patients who experience a DLT of Grade 4 non-hematological toxicity will not restart magrolimab and will be withdrawn from study drug treatment. Data from patients who restart dosing after the recovery period will not contribute to the MTD evaluation at the lower dose level. Treatment delays of more than 4 weeks (such as for an unrelated medical condition with expected recovery) must be discussed with the Medical Monitor and approved by the Sponsor.

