# 6.2.1.2. Azacitidine

#### **Dose Modifications**

Dose modification or dose delay of azacitidine may not occur for patients in the initial 28-day DLT Assessment Period in the TN/U Dose Evaluation Cohort or for the first cycle for patients in the TN/U Expansion Cohort. Dose modifications described below are in accordance with the azacitidine prescribing information with modifications. While the US prescribing information allows for dose escalation to 100 mg/m^2 after the first 2 cycles, a consistent azacitidine dose of 75 mg/m^2 is planned throughout this study. Azacitidine dose increases are not allowed without prior approval from the Medical Monitor. The azacitidine dose modifications described below are per prescribing information and serve as general recommendations. However, in standard clinical practice, azacitidine label instructions for dose reduction (based on nadir blood counts and bone marrow assessment) are not routinely followed in the clinical setting, and it appears that this part of the label has not been updated since the first approval of azacitidine in 2004. Recommendations from international groups underline the importance of maintaining azacitidine dose intensity in higher-risk MDS patients and AML patients and to avoid dose reductions, if possible (Fenaux 2010; Santini 2014; Wells 2014). Therefore, azacitidine dose modifications will follow the prescribing information below or institutional practice supported by international recommendations.

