### 11.1. Safety Analysis

All patients who receive at least 1 dose of magrolimab will be included in the safety analysis.

The DLT analysis will be conducted in the TN/U Dose Evaluation Cohort in patients who completed either at least 4 infusions of magrolimab or 4 infusions/injections of azacitidine and have been followed for the 4-week DLT Assessment Period or have experienced a DLT within 4 weeks after initiating study drug treatment.

Safety will be assessed through summaries of deaths, DLTs, AEs, changes in laboratory test results, and exposure to magrolimab.

Adverse events leading to treatment discontinuation will be listed. AEs leading to the declaration of DLTs will be listed.

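### Protocol section 11.1 admits patients to the DLT analysis on four doses of either drug, while section 3.3.4 requires four doses of both and replaces everyone else without a DLT

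*Protocol*

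**What the plan says.** Section 3.3.4 defines who is evaluable for DLT in the TN/U Dose Evaluation Cohort. There are two routes: a DLT, or sufficient exposure to both drugs in the 4-week DLT Assessment Period: "The patient completed at least 4 infusions of magrolimab and 4 infusions/injections of azacitidine". A patient who meets neither, or who withdraws before the 4 weeks are over for a reason other than a DLT, "will not be evaluable for assessment of DLT for dose review decisions and will be replaced in the cohort". Section 3.3.3 supports this: "A new patient may be enrolled whenever a patient becomes nonevaluable for DLT".

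Section 11.1 defines the DLT analysis for the same cohort and the same period. It takes "patients who completed either at least 4 infusions of magrolimab or 4 infusions/injections of azacitidine" who were followed for the 4 weeks, or who had a DLT within 4 weeks of starting study drug.

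Table 3-2 and the synopsis give the schedule. Azacitidine is given on Days 1 to 7 of each cycle. Magrolimab in Cycle 1 is "1 mg/kg on Days 1 and 4; 15 mg/kg on Day 8; 30 mg/kg on Days 11 and 15", and Table 3-2 adds a further 30 mg/kg infusion on Day 22.

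**The concern.** Both sections require 4 weeks of follow-up from a DLT-free patient. They differ in how the two drugs are joined: *and* in 3.3.4, *or* in 11.1. A patient can therefore be judged not evaluable and be replaced, yet still be counted as DLT-free in the reported analysis, possibly alongside the replacement.

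A DLT-evaluable set is meant to ensure that a patient counted as tolerating the regimen has received enough of it. With *or*, four azacitidine doses are enough, and magrolimab, the investigational drug, need hardly have been given. Safety and tolerability are primary objectives (section 2.1.1) and 11.1 promises summaries of DLTs, so the denominator should follow one rule.

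**Working it through.** The protocol states no DLT count and no number evaluable for this cohort, so there is no figure to reproduce. The check compares the two definitions and then uses the dosing schedule.

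**Step 1. The two definitions.**

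| DLT-free patient followed for 4 weeks | Section 3.3.4 | Section 11.1 |
|---|---|---|
| At least 4 magrolimab and at least 4 azacitidine doses | evaluable | counted |
| At least 4 azacitidine, fewer than 4 magrolimab | replaced | counted |
| At least 4 magrolimab, fewer than 4 azacitidine | replaced | counted |
| Fewer than 4 of each | replaced | not counted |

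I read the DLT clause in 11.1 as a route of its own, as in 3.3.4. A patient with a DLT then counts under both sections, and the disagreement is confined to the two middle rows.

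**Step 2. Magrolimab exposure in the second row.**
- Four azacitidine doses are reached on Day 4. By then two magrolimab infusions are scheduled: 1 + 1 = 2 mg/kg.
- The fourth scheduled infusion, Day 11, is the first at 30 mg/kg.
- Scheduled Cycle 1 total: 1 + 1 + 15 + 30 + 30 + 30 = 107 mg/kg.
- The first three infusions: 1 + 1 + 15 = 17 mg/kg, and 17/107 = 15.9%.

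On the scheduled doses, a DLT-free patient with three infusions or fewer has had at most 17 mg/kg and no 30 mg/kg dose, yet meets 11.1 through azacitidine.

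**Step 3. Whether such a patient can arise.** Section 6.2.1.1 gives two routes. First: "Magrolimab may be withheld if treatment-emergent and/or magrolimab-related AEs occur, which include all AEs that constitute a DLT". The events covered include DLTs but are not confined to them, so magrolimab could be withheld from a patient who has no DLT. Second, a Cycle 1 infusion may be delayed by up to 3 days for a high white cell count, and beyond that: "Further dose delay due to elevated WBC counts must be discussed and approved by the Medical Monitor". Azacitidine meanwhile continues under section 6.2.1.2: "Dose modification or dose delay of azacitidine may not occur for patients in the initial 28-day DLT Assessment Period". That restriction makes the second row of the table more plausible than the third.

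**Step 4. Direction.** Let d be the number of DLTs, n the number evaluable under 3.3.4, and m at least 1 the number of DLT-free patients admitted only through *or*. The reported rate moves from d/n to d/(n + m). It is lower when d is at least 1 and unchanged when d is 0; it cannot rise. The protocol gives none of d, n or m, so the size of the shift cannot be computed.

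**The case against.** The strongest reply is that no decision depends on 11.1. Section 3.3.4 ties its rule and the replacement to dose review, and the committee's dose decisions run on section 3.3. Section 11.1 governs reporting. The cohort is closed with 8 patients (section 11.4), and the synopsis records the recommended Phase 2 dose and schedule as selected. Section 11 prefers listings when numbers are small, section 11.8.3.1 lists DLTs, and a listing has no denominator. All of this stands and limits the severity. It does not reconcile the two definitions: nothing calls the 11.1 set a separate or sensitivity set, and 11.1 also promises DLT summaries, so a denominator remains possible.

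A second reply is that the white-cell route is remote. Six infusions are scheduled in Cycle 1, so if delayed doses are skipped, three must be missed to leave fewer than four. If they shift instead (an assumption; the protocol does not say), the fourth still falls within 28 days for a total delay of up to 28 − 11 = 17 days. Hydroxyurea or etoposide may also be used to bring the count down. This too stands: the case is possible under the text, but probably uncommon.

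A reader might infer from 8 enrolled, against up to 6 evaluable per dose level, that two patients were replaced and would re-enter through *or*. The documents do not support that. Section 3.3.2 lets the committee add patients for safety and PK information, and section 3.3.3 allows a spare fourth patient, so 8 enrolled is consistent with no replacement at all.

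**Conclusion.** Section 11.1 is wrong as written. It states an analysis set that contradicts 3.3.4 for the same cohort and period, and the protocol fixes both rules itself, so this is not detail left to the SAP. Followed literally, it can add under-exposed DLT-free patients to the reported denominator, which can only dilute the DLT rate.

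The consequence is small and limited to the reported DLT analysis. A reader might go further and infer that the selected dose rests on a diluted DLT rate. The documents do not support this: dose review used the 3.3.4 rule, and no affected patient is shown. The conclusion assumes only that 11.1 is applied literally and that its DLT clause stands alone. Severity is low: an inexpensive correction worth making before the final report.

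**What to change.** In section 11.1, replace the *either/or* exposure wording with the 3.3.4 definition: at least four magrolimab infusions and four azacitidine doses, or a DLT, in the 4-week DLT Assessment Period. A cross-reference to 3.3.4 does the same and keeps a single definition. Any DLT summary for this cohort should use that set as its denominator.

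The change is one word group, or one cross-reference. It needs no new data and alters no dosing decision. If made as a protocol amendment it goes through the usual ethics submission, so it is best carried with the next one.

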### 11.2. Efficacy Analysis

All patients who receive at least 1 dose of magrolimab will be included in the efficacy analysis except for those endpoints that are applicable only to patients who achieved a response. In addition, an evaluable patient efficacy analysis will also be performed on all enrolled patients who receive at least 1 dose of magrolimab and have at least 1 disease response assessment or who died before the first disease response assessment.

## 11.3. Pharmacokinetics Analysis

The PK analysis will be conducted on all enrolled patients treated with magrolimab (and/or azacitidine if appropriate) whose PK blood samples are collected during the study and who have measurable concentrations of magrolimab (and/or azacitidine if appropriate).

## 11.4. Sample Size Determination

The number of patients planned for inclusion in this trial is up to a total of approximately 287 patients evaluable for efficacy, as follows:

- R/R Safety Cohort: 10 patients
- R/R Expansion Cohort: Up to 36 patients
- R/R MDS Magrolimab Monotherapy Cohort: 23 patients
- TN/U Dose Evaluation Cohort: Up to 18 patients
- TN/U Expansion Cohort: Up to 172 patients, including
  - Original 30 TN/U Expansion (enrolled 18 AML and 16 MDS patients, including 4 replacement patients)
  - At least 92 MDS patients (including the original 16 MDS patients enrolled in the original TN/U Expansion), of whom at least 56 patients will be on Q2W dosing. The overall MDS expansion to 92 patients will be considered the MDS Registrational Cohort.
  - Up to 62 TP53 mutant AML patients (i.e., 12 original TP53 mutation AML patients, plus 20 additional TP53 mutant AML patients added per CTSC decision in September 2019, plus 30 additional TP53 mutant AML patients per CTSC decision July 2020)
- RBC Transfusion-dependent Low-risk MDS Cohort: Up to 20 patients
- Rollover Cohort: Up to 8 patients

For the R/R Safety Cohort, 10 patients have been enrolled as of the approval of Amendment 5 for evaluation of safety of magrolimab monotherapy.

For the R/R Safety Cohort and Expansion Cohort, approximately 46 patients may be enrolled, including 10 patients treated in the safety run-in cohort and 36 patients treated in the expansion cohort. For the R/R Safety Cohort, 10 patients were enrolled and this cohort was closed to further enrollment as of Amendment 3. Based on safety and efficacy data, the CTSC may decide to expand the R/R Expansion Cohort to include additional patients. An ORR of 17% has been reported in patients with R/R AML who have been treated with azacitidine (Itzykson 2015). For an estimated response rate of 33% or higher, 36 patients would provide a 95% confidence interval, with the lower bound to exclude 18.6%, the azacitidine monotherapy efficacy rate.

Per FDA feedback, a magrolimab monotherapy cohort in R/R MDS will be evaluated to further define the activity of magrolimab to the contribution of magrolimab+azacitidine in MDS to support a potential single-arm approval of magrolimab+azacitidine in MDS. Patients will be enrolled in a Simon's 2-stage design. With a 1-sided significance level of 0.05 and 80% power, the null hypothesis that the magrolimab monotherapy ORR is 9% will be tested against the alternative of 30%. In the first stage, 11 patients will be enrolled. If there are 1 or fewer responses observed in these 11 patients, the cohort will be stopped. Otherwise, 12 additional patients will be accrued, for a total of 23. This cohort was stopped after 11 patients enrolled per CTSC decision in October 2020. The null hypothesis will be rejected if 5 or more responses are observed in 23 patients.

For the TN/U Dose Evaluation Cohort, up to 18 patients can be enrolled based on a 3+3 dose de-escalation design, assuming 3 potential dose cohorts with a maximum of 6 patients treated per cohort. For the TN/U Dose Evaluation Cohort, 8 patients were enrolled and this cohort was closed to further enrollment as of Amendment 5.

For the TN/U Expansion Cohort, a total of up to 172 patients may be enrolled. An initial sample size of 30 patients was proposed so that the 95% confidence interval of the desired 35% or higher CR rate would exclude a known CR rate of 17.85% for azacitidine alone. This sample size calculation was based on inclusion of both TN/U AML and higher-risk MDS patients. For the higher-risk, untreated, MDS-only Expansion Cohort, an evaluation will occur after 36 patients have reached the first response

assessment (Cycle 3 Day 1); however, enrollment will continue and not be paused in the interim. A sample size of 36 patients provides 80% power to reject the null hypothesis that the CR rate is 16.5% or lower at 2-sided 0.05 significant level, assuming the true magrolimab + azacitidine CR rate is at least 35.5% (19% improvement). The null CR rate of 16.5% is based on the pivotal randomized trial leading to azacitidine approval in MDS reanalyzed by IWG 2000 criteria (Silverman 2006), where the upper bound of the 1-sided 95% confidence interval for azacitidine CR rate is 16.5%, with a point estimate of 10%. Based on Amendment 6 and FDA feedback for a single-arm trial to support a potential BLA, the sample size of the TN/U MDS-only Expansion Cohort for untreated, higher-risk MDS patients was further increased to include a cohort of 56 patients with MDS at a magrolimab Q2W dosing regimen. A sample size of 56 patients provides 80% power to reject the null hypothesis that the CR rate is 16.5% at a 2-sided 0.05 significant level, assuming the true magrolimab+azacitidine CR rate is at least 31.5%. The null CR rate of 16.5% is based on the same assumption for azacitidine monotherapy as above. A combined planned sample size of 92 patients for the MDS Registrational Cohort will provide an 80% power to reject the updated null CR rate of 23.5% at a 2-sided 0.05 significant level, assuming the true magrolimab+azacitidine CR rate is 36.5%.

Per the CTSC decision in September 2019 and Amendment 6, a subcohort of TP53 mutant TN/U AML patients was added. Initially, 12 patients and then an additional 20 patients will be enrolled. Analysis of these patients will include all TP53 mutant patients meeting subcohort eligibility enrolled prior to the Amendment/CTSC decision. A sample size of 32 patients was selected to evaluate the initial efficacy of magrolimab+azacitidine as compared to available therapies (most notably venetoclax+hypomethylating agents) in TP53 mutant AML. While venetoclax in combination with hypomethylating agents (azacitidine or decitabine) is approved in newly diagnosed AML patients who are ineligible for intensive chemotherapy, their efficacy in TP53 mutant AML patients is limited. Per a recent report, the CR+CRi rate of venetoclax+hypomethylating agent in TP53 mutant AML was 47%, with a median duration of CR of 5.6 months and a median overall survival of 7.2 months (DiNardo 2019). In contrast, in all-comer AML patients, the CR+CRi rate was 67% with

a median duration of CR of 11.3 months and a median overall survival of 17.5 months. Assuming an observed magrolimab+azacitidine ORR of 59% for a sample size of 32 patients, the 1-sided 90% confidence interval will have a lower bound of 46.5%, which excludes a control ORR of 46%. Based on emerging data, the CTSC may decide to enroll additional patients for further safety, efficacy, or dosing information. Per CTSC decision in July 2020 and captured in Amendment 7, an additional 30 TP53 mutant AML patients were enrolled for the TN/U Expansion Cohort (n = 62).

For the RBC Transfusion-dependent Low-risk MDS Cohort, approximately 20 patients will be enrolled. Initially, 6 patients will be enrolled with a safety evaluation after all 6 patients complete at least Cycle 2 Day 15 treatment. This safety evaluation is being conducted given that a 60 mg/kg dose of magrolimab will be administered starting in Cycle 2, of which this highest dose has not yet been tested in MDS patients. However, an equivalent dose of 60 mg/kg given in 1 week (30 mg/kg twice weekly) has already been administered to MDS and AML patients in this trial and has been well tolerated. The CTSC will then evaluate based on the aggregate safety profile in these 6 patients and determine whether enrollment should proceed to the remaining 14 patients. If so, these 14 patients can be simultaneously enrolled. Based on emerging data, the CTSC may decide to enroll additional patients for further safety, efficacy, or dosing information. These may be enrolled as either magrolimab monotherapy or in combination with azacitidine.

For the Rollover Cohort, 1 eligible patient from the Phase 1 study (SCI-CD47-002) is now enrolled in this study, and this cohort was closed to further enrollment as of Amendment 3.

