The R/R Cohorts consist of 2 cohorts: 1) an R/R Safety and Expansion Cohort, and 2) an R/R MDS Magrolimab Monotherapy Expansion Cohort. The R/R Safety and Expansion Cohort consists of an initial evaluation of magrolimab monotherapy in R/R MDS/AML patients, followed by an expansion cohort of magrolimab + azacitidine in R/R MDS/AML patients. As of Amendment 3, in the first stage, patients in the R/R Safety Cohort have been treated at the maintenance dose of 30 mg/kg twice weekly; going forward, these patients will be treated weekly at the maintenance dose of 30 mg/kg, as determined by the Clinical Trial Steering Committee (CTSC) based on clinical, PK, and PD data. This safety run-in will confirm the safety profile of magrolimab monotherapy at this dose level in an expanded R/R population. Approximately 30 days after enrollment is completed in the R/R Safety Cohort, the CTSC will assess the safety data to determine whether enrollment may begin in the TN/U Dose Evaluation Cohort. In addition, the CTSC will also determine whether enrollment will proceed to an initial 36-patient R/R Expansion Cohort, based on safety and efficacy data, which will be conducted with magrolimab in combination with azacitidine as per Amendment 5. Based on emerging data, the CTSC may decide to enroll additional patients beyond 36 for further safety, efficacy, or dosing information.

The R/R MDS Magrolimab Monotherapy Cohort was added in Amendment 6. Per FDA feedback, a magrolimab monotherapy cohort in R/R MDS will be evaluated to further define the activity of magrolimab to the contribution of magrolimab + azacitidine in MDS to support a potential single-arm approval of magrolimab + azacitidine in MDS. Patients will be enrolled in a Simon's 2-stage design to evaluate for potential futility. Patients who do not achieve an objective response with magrolimab monotherapy at the protocol-defined first response assessment may have azacitidine added by discretion of the Principal Investigator with Sponsor approval, according to the schedule of azacitidine outlined in the R/R cohorts.

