## 4. PATIENT SELECTION AND ENROLLMENT

## 4.1. Study Entry Criteria

## 4.1.1. Inclusion Criteria

## **All Patients:**

- 1. Meets the criteria below for the appropriate cohort:
  - a. All R/R Cohorts (meets i or ii):
    - i. Pathologically confirmed AML (defined by 2017 ELN classification; Döhner 2017) relapsed or refractory to a prior therapy with either a hypomethylating agent (such as azacitidine or decitabine), non-intensive chemotherapy (such as low-dose cytarabine arabinoside), and/or venetoclax. Treatment is limited to 1 prior line of therapy. Hematopoietic

- stem cell transplant for patients in remission would not be counted as a line of therapy for AML, or
- ii. Confirmed MDS defined according to World Health Organization (WHO) classification that is either refractory to hypomethylating agent (defined as disease progression per IWG 2006 criteria [Cheson 2006] at any time after initiation of a hypomethylating agent or failure to achieve an objective response by IWG 2006 criteria after 4 cycles) or is relapsed or intolerant to prior therapy with either a hypomethylating agent, non-intensive chemotherapy, or targeted therapy. Treatment is limited to 1 prior line of hypomethylating agent therapy (including investigational hypomethylating agents) for all R/R MDS patients.
- iii. R/R MDS Magrolimab Monotherapy Cohort: Inclusion criterion ii above applies.

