## 4.1.2. Exclusion Criteria

- 1. Prior treatment with CD47 or SIRPα-targeting agents (with exception of magrolimab for patients in the Rollover Cohort).
- 2. Prior anti-leukemic therapies including, but not limited to, chemotherapy (with the exception of hydroxyurea or oral etoposide), targeted therapies, immunotherapy, or radiotherapy within 4 weeks prior to Day 1 magrolimab dosing. NOTE: Localized non-central nervous system (non-CNS) radiotherapy, previous hormonal therapy with luteinizing hormone-releasing hormone (LHRH) agonists for prostate cancer, and treatment with bisphosphonates and receptor activator of nuclear factor kappa-B ligand (RANKL) inhibitors are not criteria for exclusion.
- 3. **TN/U Cohorts only**: Any prior anti-leukemic therapy (excluding hydroxyurea or oral etoposide), prior treatment with hypomethylating agents and/or low dose cytarabine.
- R/R Expansion Cohort, R/R MDS Magrolimab Monotherapy Cohort, TN/U
   Cohorts, and RBC Transfusion-dependent Low-risk MDS Cohort only:
   Contraindications to azacitidine, including advanced malignant hepatic tumors or known hypersensitivity to azacitidine or mannitol.
- 5. Acute promyelocytic leukemia.
- 6. Known inherited or acquired bleeding disorders.
- 7. Previous allogeneic hematopoietic stem cell transplant within 6 months prior to enrollment, active graft versus host disease (GVHD), or requiring transplant-related immunosuppression.
- 8. Clinical suspicion of active CNS involvement by leukemia.
- 9. Significant medical diseases or conditions, as assessed by the Investigators and Sponsor, that would substantially increase the risk-benefit ratio of participating in the study. This includes, but is not limited to, acute myocardial infarction within the last 6 months, unstable angina, uncontrolled diabetes mellitus, significant active infections, and congestive heart failure New York Heart Association (NYHA) Class III-IV.
- 10. Second malignancy, except treated basal cell or localized squamous skin carcinomas, localized prostate cancer, or other malignancies for which patients are not on active anti-cancer therapy as defined in Exclusion Criterion 2.

- 11. History of psychiatric illness or substance abuse likely to interfere with the ability to comply with protocol requirements or give informed consent.
- 12. Pregnancy or active breastfeeding.
- 13. Known active or chronic hepatitis B or C infection or human immunodeficiency virus (HIV).

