### 11.8. Statistical Methods

All analyses will be conducted separately for patients by indication in the R/R Cohorts, the TN/U Cohorts, and the Rollover Cohort, unless otherwise mentioned. Additional analyses may be conducted separately for the R/R Safety Cohort alone and TN/U Dose Evaluation Cohorts. Combined safety analyses may be conducted for patients in both monotherapy cohorts (the R/R Safety Cohort, R/R MDS Cohort, and Rollover Cohort, where applicable), as well across the study on all treated patients. Statistical analyses

will be performed separately for the patients treated with magrolimab in combination with azacitidine in the TP53 TN/U AML Cohort and RBC Transfusion-dependent Low-risk MDS Cohort, as well as in the untreated higher-risk MDS cohort as a potential pivotal single-arm study to support a potential BLA in higher-risk untreated MDS.

For continuous variables, the mean, standard deviation, median, and ranges will be provided. For categorical variables, the frequency and percentage in each category will be provided, along with 95% confidence intervals for primary and secondary efficacy endpoints. For time-to-event variables, the Kaplan-Meier (KM) estimates and corresponding 2-sided 95% confidence intervals for the median will be provided, when appropriate. The KM plots may also be provided. Details regarding the statistical analysis to be conducted, including the handling of missing data and patient withdrawal, will be provided in the SAP.

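### The R/R Expansion Cohort's 36-patient precision is stated against an R/R AML benchmark, but the 36 places are shared with R/R MDS and analysed by indication

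*Protocol*

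**What the plan says.** Section 11.4 (repeated in the synopsis) gives the size as "R/R Expansion Cohort: Up to 36 patients". The benchmark is specific to one disease: "An ORR of 17% has been reported in patients with R/R AML who have been treated with azacitidine". The precision statement follows: "For an estimated response rate of 33% or higher, 36 patients would provide a 95% confidence interval". The same sentence then names the figure that this interval is meant to clear and says what that figure represents: "with the lower bound to exclude 18.6%, the azacitidine monotherapy efficacy rate".

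Section 3.1 describes the cohort differently: the safety run-in is "followed by an expansion cohort of magrolimab + azacitidine in R/R MDS/AML patients". Inclusion criterion 1a in Section 4.1.1 admits R/R AML under (i) and R/R MDS under (ii). Neither Section 3.2 nor Section 11.4 sets a minimum or maximum for either disease.

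On analysis, Section 11.8 says "All analyses will be conducted separately for patients by indication in the R/R Cohorts", subject to exceptions mentioned elsewhere, and Section 11 likewise has summaries presented by indication and cohort. No pooled AML and MDS efficacy analysis of the R/R Expansion Cohort is mentioned.

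**The concern.** The justification uses the full 36 as its denominator and an R/R AML rate as its comparator. The analysis splits the 36 by disease, so the group to which the benchmark applies is smaller than the group from which the bound was computed, unless no MDS patient enrols. For R/R MDS, the protocol gives no azacitidine benchmark at all.

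Pooling does not solve this. Under Section 10, AML ORR counts CR, CRi, CRh, PR and MLFS. MDS objective response also counts hematologic improvement. A pooled rate would set a mixed endpoint against an AML figure.

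At stake is how the result is read. The cohort is single-arm, and its stated rationale is that the interval separates the combination from azacitidine alone. A report repeating that rationale could claim separation that the AML data do not have, or could obtain it from a pooled rate that the benchmark does not describe.

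**Working it through.** **Inputs.** From Section 11.4: n = 36, response rate 33% (12/36), 95% interval, stated lower bound 18.6%, benchmark 17% in R/R AML. The number of AML patients is not in the protocol, so the values below 36 are assumptions shown as a range.

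**Formula.** The exact (Clopper-Pearson) two-sided 95% lower bound for x responders in n is the 0.025 quantile of a Beta(x, n − x + 1) distribution.

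**The plan's own figure.** x = 12, n = 36: the 0.025 quantile of Beta(12, 25) is 18.56%, which rounds to the stated 18.6% (upper bound 50.97%). Other intervals do not give it: Wald 17.9%, Wilson 20.2%, one-sided 95% exact 20.5%. So the protocol used the exact two-sided interval on all 36 patients.

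**The same calculation at smaller AML numbers, one-third responding.**

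| AML patients (assumed) | Responders | Exact 95% lower bound | Excludes 17%? |
|---|---|---|---|
| 36 | 12 | 18.6% | yes |
| 33 | 11 | 18.0% | yes |
| 30 | 10 | 17.3% | yes |
| 27 | 9 | 16.5% | no |
| 24 | 8 | 15.6% | no |
| 18 | 6 | 13.3% | no |

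Three MDS patients (36 − 33) already take the AML bound below the stated 18.6%. Nine (36 − 27) take it below the 17% benchmark.

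**Observed rate needed to exclude 17% in the smaller groups.** 10/27 (37.0%) gives 19.4%, 9/24 (37.5%) gives 18.8%, and 7/18 (38.9%) gives 17.3%. In each case that is one responder more than one-third.

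**The 18.6% label.** Section 11.4 reports an azacitidine ORR of 17%, then calls 18.6% the azacitidine monotherapy efficacy rate. Since 18.6% is the computed bound for 12/36, the second label attaches a result of the calculation to the comparator.

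**The case against.** The case for leaving this alone is that the cohort is exploratory: it has no hypothesis test, alpha level or go/no-go rule tied to the bound. The protocol speaks of 33% or higher, and one extra responder restores exclusion of 17% at 27, 24 or 18 AML patients. The split is unknown, the CTSC may enrol beyond 36, and Section 11.8 allows exceptions to analysis by indication. Under a Wilson interval 17% would still be excluded at 27 (18.6%) and 24 (18.0%), though not at 18 (16.3%). The cohort is closed to enrollment (Table 7-1), and Section 11.8 already requires 95% intervals, which will reflect the actual numbers.

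Much of this stands as a limit on size. It does not remove the point. The size, the eligibility and the grouping are all fixed in this protocol, so the mismatch is not a detail left to the SAP. No exception to analysis by indication is stated for this cohort's efficacy. Wilson does not reproduce the protocol's own figure. Closure means the correction concerns reporting, not recruitment. For the TN/U Expansion Cohort, Section 11.4 says its initial calculation covered AML and MDS together; the R/R paragraph says nothing of the kind.

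A reader might go further in three ways that the documents do not support.

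- Criterion 1a mixes patients by prior hypomethylating-agent history, including MDS that "or is relapsed or intolerant to prior therapy with either a hypomethylating agent, non-intensive chemotherapy, or targeted therapy". One might infer that this mix also costs precision. It does not: interval width depends on responders and number analysed. Whether the mix weakens comparability with the 17% depends on prior therapy in the cited azacitidine study, which the protocol does not describe.
- One might infer that responses in refractory patients cannot be due to azacitidine. Criterion 1a(ii) counts non-response after 4 cycles as refractory, while Section 3.3.1 recommends at least 6 cycles of azacitidine, and the prior agent may have been decitabine.
- One might infer that admitting intolerant patients contradicts Exclusion 4, "Contraindications to azacitidine, including advanced malignant hepatic tumors or known hypersensitivity to azacitidine or mannitol". That list is introduced as inclusive, not exhaustive, and applies alongside 1a(ii).

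**Conclusion.** The 18.6% bound is correctly computed but attached to the wrong group. As a statement about R/R AML against a 17% azacitidine ORR, it holds only if all 36 patients have AML, or if the CTSC enlarges the cohort until AML reaches 36.

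With one-third responding and the exact interval that the protocol itself used, the AML lower bound lies between 18.0% and 13.3% for 33 down to 18 AML patients. It no longer excludes 17% at 27 or fewer. These sizes rest on an assumed split. Near the threshold the shortfall is small: 0.5 percentage points at 27 (17.0 − 16.5). The loss comes entirely from dividing the cohort by disease. The point is worth correcting because it changes a stated design figure and its comparator, but it does not invalidate the cohort.

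**What to change.** In Section 11.4 and the synopsis:

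1. Tie the 17% azacitidine ORR to the R/R AML subset.
2. Restate the 95% lower bound at the number of AML patients enrolled, or show it over a range of AML numbers as in the table above.
3. State that R/R MDS in this cohort is descriptive, and that no pooled AML and MDS response rate is compared with 17%.
4. Call 18.6% the lower bound for 12/36 and stop labelling it the azacitidine rate.

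The cost is a few sentences, with no new patients or data. The drawback is that the stated precision becomes less favourable. A table of response by prior hypomethylating-agent status is optional and belongs in the SAP.
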